5.3. HANDLING OF VALUES BELOW (OR ABOVE) A THRESHOLD

5.3.1. Safety Data

Values below (above) the detection limit will be imputed by the value of the detection limit itself. Listings will always present the original value.

Example: if the database contains values like “<0.04”, then for the descriptive statistics the value of the detection limit (0.04) shall be used. A value like “>1000” will be imputed by “1000”.

5.3.2. PK Data

Values below the quantification limit will be imputed by 0 for PK parameters calculation and descriptive statistics calculation except for geometric mean and geometric CV% where it will be imputed as LLOQ (lower limit of quantitation)/2 and listed as “BLOQ”.

For the C_{trough} , values BLOQ will be imputed by LLOQ/2 when computing inferential statistics and between-group comparisons.

5.3.3. PD Data

PD data correspond to all [REDACTED] biomarkers and biomarkers [REDACTED] that have been collected as exploratory assessments.

Values below the lower detection limit will be imputed by the half of value of the detection limit itself. Values above the upper detection limit will be imputed by the value of the upper detection limit itself. Listings will always present the original value.

5.4. HANDLING OF MISSING DATA

5.4.1. Observed Cases (OC)

No imputation is done of missing values.

5.4.2. Last Observation Carried Forward (LOCF)

For efficacy parameters (see section 9), a LOCF analysis will be performed carrying forward the last nonmissing result (even if this would be a baseline result) except for the FU timepoint (FU timepoint will always provide observed cases values).

As spirometry has been assessed predose and between 1h and 2h post-dose at Day 1 and Day 29, LOCF imputation should be adapted with the following rule:

- If missing value corresponds to a predose timepoint, then the last nonmissing result assessed at pre-dose will be used for LOCF imputation.
- If missing value corresponds to a post dose timepoint, then the last nonmissing result assessed at post dose will be used for LOCF imputation (if there is no last non missing timepoint assessed at post-dose, then baseline value will be used).

5.4.3. Handling of Missing Date(Time) or Partially Known Date(Time)

No imputation will be done of missing date(time) fields, nor of the missing parts of partially known date(time) fields. When needed (e.g., a double phase allocation), a worst-case selection will be made.

5.5. HANDLING OF OUTLIERS

All measured values will be included in the analyses.

5.6. HANDLING OF SECONDS IN DATETIME FIELDS

If a datetime field contains seconds, these will be cut off (i.e., rounded down to the minute) prior to data analysis. The analysis will only use the date and time up to the minute.

6. SOFTWARE AND PROCEDURES

6.1. SOFTWARE

SAS version 9.4 will be used for programming.

SigmaPlot® 12.5, or higher (Systat Software, Inc., San Jose, California, United States) will be used for PK figures.

Phoenix WinNonlin® 6.4, or higher will be used for the figures and parameter calculation.

6.2. PROCEDURES

Analyses will comply with ICH regulations, in particular: (ICH-E3) , (ICH-E6) and (ICH-E9).

The following Galapagos SOPs will be followed:

- SOP-CLI-001: Developing Clinical Study Documents (version 1.0)
- SOP-CLI-003: Managing Data Processing Activities (version 1.0)
- SOP-CLI-004: Managing DSMB Activities (version 1.0)

The following CRO STAT SOPs will be followed:

- CS_OP_BS001: Statistical Principles
- CS_OP_BS0216: Ensuring Quality in Biostatistical Deliverables
- CS_WI_BS002: Randomization
- CS_WI_BS003: Unblinding
- CS_WI_BS005: Statistical Analysis Plans (Covering Table Shells)
- CS_WI_BS009: Interim Analysis
- CS_WI_BS011: Analysis Sets
- CS_WI_BS013: Derived Datasets
- CS_WI_BS014: Statistical Output
- CS_WI_BS015: Approaches to QC
- CS_WI_BS020: Handling Data transfer.

The following PK SOPs will be followed, unless otherwise specified

- PI_OP_PK0206: Pharmacokinetic/Pharmacodynamic Analysis
- PI_WI_BS0214: Generation of a WinNonlin Analysis Data File
- PI_WI_BS0217: Rounding of Numerical Values
- PI_WI_PK_0202: Pharmacokinetic and Pharmacodynamic Analysis Procedures
- PI_WI_PK0205: Standardization of Pharmacokinetic and Pharmacodynamic Symbols

6.3. FORMATS

Because the locked data is in CDISC SDTM format, the derived data will be following CDISC ADaM 2.1 ADAMIG version 1.0 format.

Tables, listings and figures will follow the Mock TLFs, as provided in a separate document.

7. STATISTICAL METHODS

7.1. PLANNED ANALYSES, PROTOCOL AMENDMENTS INCLUDED

7.1.1. General Statistical Considerations

Summary tabulations will display the number of observations, mean, standard error, median, minimum, and maximum for continuous variables, and the number and percent category for categorical data. Tabulated descriptive statistics and graphical data displays may be used to summarize the data. Inferential statistics will be interpreted at the 2-sided 5% level.

7.1.2. Analyses of Demographics and Baseline Characteristics

Subject disposition, protocol deviations, demographics, baseline characteristics, medical history, concomitant therapies, and exposure will be analyzed descriptively and/or listed and presented overall and by treatment group.

7.1.3. Analyses of Efficacy Parameters

Descriptive statistics of actual values, changes from baseline (pre-dose on Day 1), and percent changes from baseline will be provided.

An analysis of covariance (ANCOVA) model on the changes from baseline at each time point, with treatment as factor and baseline value as covariate, will be applied to the following parameters:

- Sweat chloride concentration;
- FEV₁;
- CFQ-R scores.

Between-group comparisons will be done for each GLPG2222 group versus the pooled placebo group (if the study is performed in both Cohorts A and B) or versus placebo in Cohort A (if the study is only performed in Cohort A).

Missing data will be imputed, also for subjects who prematurely discontinue the study. The primary imputation method will be the last-observation-carried-forward. An observed-case analysis will also be performed.

A sensitivity analysis will be performed by using non-parametric tests. The GLPG2222 groups and pooled placebo group (if the study is performed in both Cohorts A and B) or the GLPG2222 groups and placebo in Cohort A (if the study is only performed in Cohort A) will be compared using a Kruskal-Wallis test (overall treatment effect) and Wilcoxon rank sum tests (pairwise comparisons versus the corresponding placebo group).

Additional exploratory analyses and graphical presentations have been described in this SAP to better understand the data.

7.1.4. Analyses of Safety Data

Adverse events will be fully described and coded according to the Medical Dictionary for Regulatory Activities (version 20.0). Physical examination, weight, vital signs, oxygen saturation by pulse oximetry, 12-lead ECG, spirometry, and clinical safety laboratory data will be analyzed descriptively. Changes from baseline (pre-dose on Day 1) and shifts according to normal ranges will be presented as well. Analysis will be done per treatment group.

7.1.5. Pharmacokinetics Analyses

Descriptive statistics will be calculated by dose level and day for the plasma concentrations and PK parameters of GLPG2222.

Plasma concentrations of GLPG2222 will also be analyzed using a population PK approach including the assessment of covariates influencing the PK in CF subjects. The relation between exposures and selected efficacy and safety endpoints will also be investigated, if relevant. The modeling approach will be described and reported separately.

7.1.6. Exploratory Biomarkers

Exploratory biomarker data (███████████) will be analyzed using descriptive statistics of actual values, changes from baseline (pre-dose on Day 1), and percent changes from baseline.

7.1.7. Apical Expression of F508del CFTR (Optional Substudy)

For subjects who participate in the optional substudy, data on apical expression of F508del CFTR will be analyzed using descriptive statistics of actual values, changes from baseline (pre-dose on Day 1), and percent changes from baseline.

7.2. CHANGES TO THE PLANNED ANALYSES, NOT COVERED BY PROTOCOL AMENDMENTS

7.2.1. Changes before Database Lock

Not Applicable

7.2.2. Changes after Database Lock

Not Applicable

8. DEFINITIONS OF GENERAL ANALYSIS TABLES, LISTINGS AND FIGURES

8.1. SUBJECT DISPOSITION

Listing 16.2.1.1: Subject disposition: Randomization

Listing of subject numbers and randomization groups, any information on code breaking.

All discrepancies (as-randomized versus as-treated) will be flagged.

Population: all enrolled.

Listing 16.2.1.2: Subject disposition: Country and site identification

Listing of country and site with the list of all subjects that were enrolled in this study.

Population: all enrolled.

Table 14.1.1.1: Subject disposition: Analysis populations

Tabulation per treatment group (and overall) of the number of subjects in each of the analysis populations defined in section 2.

Population: all screened subjects.

Table 14.1.1.2: Subject disposition: Tabulation of the number of subjects at each time interval

Tabulation per treatment group (and overall) and per analysis time point of the number of subjects with data.

Population: safety.

Listing 16.2.1.3: Subject disposition: Number of days in study

Listing per treatment group, per subject and per time point the number of days in study at the time of the analysis time point (derivation of these “days”: see section 4.1).

Population: safety.

Table 14.1.1.3: Subject disposition: First and last date in the study

List the following:

- Date of the first signature on study ICF
- Date of first and last screening
- Date of first study drug administration
- Last visit date (all visits; including unscheduled visits)
- Last date of contact in the study with any subject.

Population: all screened.

Listing 16.2.1.4: Subject disposition: Study termination

Listing per treatment group and per subject of the reason for completion/discontinuation and the number of days since first study drug administration at study termination. In case the discontinuation was due to AE, the AE preferred term will be presented in this listing. If there is a (verbatim) explanation on the discontinuation reason, this will also be presented in this listing.

Population: safety.

Listing 16.2.1.5: Subject disposition: Study analysis periods

Listing per treatment group and per subject of the analysis periods in the study, together with the start and end dates of each analysis period. With the date of first and last use of study drug, and the study termination date. (Analysis periods: see section 4.2)

Population: safety.

8.2. PROTOCOL DEVIATIONS AND ELIGIBILITY

Listing 16.2.2.1: Protocol deviations

Listing per treatment group and per subject of all protocol deviations, with indication major / minor.

Population: safety.

Listing 16.2.2.2: Eligibility criteria: Violations

Only violated in- and exclusion criteria will be listed per treatment group and per subject.

Population: safety.

Listing 16.2.2.3: Final eligibility statements

Listing per treatment group and per subject of the final eligibility statements at screening and at day 1.

Population: safety.

8.3. SUBJECTS EXCLUDED FROM ANALYSIS

Note that for the PK data there is a specific PK data handling listing. PK is therefore not included in this section, but is in section 10.

Listing 16.2.3.1: Subjects excluded from the safety analysis

Listing of all subjects that were not treated: the study termination reason and/or the reason for being a no-treatment subject will be listed, whichever is available.

Population: all screened subjects population, minus the Safety population.

Listing 16.2.3.2: Subjects excluded from the efficacy ITT analysis

Listing of all subjects that were exposed but who were not included in the ITT population: the study termination reason and the reason for being excluded will be listed.

Population: Safety population, minus the ITT population.

8.4. DEMOGRAPHICS AND BASELINE DISEASE CHARACTERISTICS

8.4.1. Parameters

- Gender
- Age at the moment of signing the ICF (years): the age is not recalculated when already available in the database
- Date of birth: only listed
- Date of signing the ICF: only listed
- Race
- Ethnicity
- Height (cm)
- Weight (kg) at screening and baseline
- Body mass index BMI = (weight in kg) / (height in m)² (kg/m²), at screening and baseline: the BMI will be recalculated and rounded to the first decimal, even when already available in the database. The original BMI will not be used in that case
- BMI categorized as:
 - ≤ 18.5 kg/m²
 -]18.5,25.0] kg/m²
 -]25.0,30.0[kg/m²
 - ≥ 30.0 kg/m²
- Childbearing potential: yes / no, no: tubal ligation / total hysterectomy / other. Only listed

8.4.2. Analysis

Table 14.1.3.1: Demographic data: Descriptive statistics

Continuous parameters: descriptive statistics per treatment group (and overall).

Categorical parameters: frequency tabulation per treatment group (and overall).

No formal comparison between the treatment groups is planned.

Population: the table will show

- safety
- ITT.

Table 14.1.3.2: Demographic data: Sub-group analyses: Descriptive statistics

The following sub-groups will be shown:

- By target C_{trough} at Day 15
- By target C_{trough} at Day 29
- By target C_{trough} at Day 15 and 29
- By sweat chloride (from arm with greatest volume) at baseline
- By sweat chloride (mean value from both arms) at baseline
- By %FEV1 at baseline

Population: the table will show

- safety
- ITT.

Table 14.1.3.3: Demographic data: Pooled analyses: Descriptive statistics

The following sub-groups will be shown:

- By target C_{trough} at Day 15
- By target C_{trough} at Day 29
- By target C_{trough} at Day 15 and 29

Population: the table will show

- safety
- ITT.

Listing 16.2.4.1: Demographic data

Listing per treatment group and per subject of all demographic parameters.

Population: safety.

Table 14.1.3.4: Baseline laboratory data: Tabulation of normal range

Frequency tabulation per lab test of the baseline result, categorized as low/normal/high according to the normal ranges (see section 13.2.4).

Population: Safety.

Table 14.1.3.5: Baseline ECG data: Tabulation of the normal range

Frequency tabulation per parameter (QT, QTcF) of the baseline result, categorized as (same as in section 13.3.4):

- ≤ 450 ms
- $]450,480]$ ms
- $]480,500]$ ms
- > 500 ms

Population: Safety.

Table 14.1.3.6: Baseline vital signs data: Tabulation of the normal range

Frequency tabulation per parameter of the baseline result, categorized as low/normal/high according to the normal ranges (see section 13.4.3).

Population: Safety.

Table 14.1.3.7: Baseline physical examination: Tabulation of the normal range

Frequency tabulation per CRF body system of the baseline result, categorized as normal/abnormal.

Population: Safety.

Table 14.1.3.8: Baseline pulse oximetry data: Tabulation of the normal range

Frequency tabulation per parameter of the baseline result, categorized as low/normal according to the normal ranges (see section 13.5.3).

Population: Safety.

8.5. BASELINE DISEASE CHARACTERISTICS

8.5.1. Parameters

- Duration of CF (years) = $\frac{(\text{date of initial diagnosis}) - (\text{date of signing the ICF}) + 1}{365.25}$, rounded to the nearest integer. If the date of initial diagnosis is incomplete, then the following rules will be applied: Missing day: use the first of the month. Missing month: use January.
- Screening and baseline sweat chloride
- Change in sweat chloride (baseline – screening)
- Screening and baseline %FEV1
- Change in %FEV1 (baseline – screening)
- Mutation F508del (on both allele): Yes/No
- Number of exacerbations requiring hospitalization and/or intravenous antibiotics in the last 12 months.
- Currently have an infection with pseudomonas aeruginosa: yes / no
- Currently on inhaled antibiotics: yes / no
- Sweat categorized at baseline: <40, [40,50[, [50,60[, >=60
- %FEV1 categorized at Baseline: <40, [40,50[, [50,70[, [70,90[, >= 90
- Sweat categorized at screening: <40, [40,50[, [50,60[, >=60
- %FEV1 categorized at screening: <40, [40,50[, [50,70[, [70,90[, >= 90

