5.2.2. Inclusion Criteria

Subjects who meet all of the following criteria are eligible for the study.

1. Male or female subject \geq 18 years of age on the day of signing the ICF.
2. A confirmed clinical diagnosis of CF and homozygous for the F508del CFTR mutation (documented in the subject's medical record or CF registry).
3. Weight \geq 40 kg during the screening period.
4. Stable concomitant medication regimen for at least 4 weeks prior to the first study drug administration and continuing the same regimen for the duration of the study.
5. FEV₁ \geq 40% of predicted normal for age, gender and height at screening (pre- or post-bronchodilator). The spirometry test must meet the criteria for acceptability and repeatability as defined in the 2005 American Thoracic Society/European Respiratory Society (ATS/ERS) guidelines on standardization of lung function testing. If screening spirometry measurements fail to meet these criteria in the first 3 efforts, up to 8 repeat spirometry efforts may be performed. If repeat values of the individual assessment(s) satisfy the eligibility criteria and are completed within the screening window, then the subject is eligible for the study (see Section 6.3.2).

6. Male and female subjects of childbearing potential must agree to use highly effective contraceptive measures as described in Section 5.2.6.2.
7. Understand and comply with protocol-specific requirements and instructions.
8. Able and willing to give voluntary written informed consent and willing to adhere to the prohibitions and restrictions (see Section 5.2.6). The ICF, as approved by the Independent Ethics Committee (IEC)/Institutional Review Board (IRB), must be signed before any study-related procedures and/or assessments are performed.

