6.2. INITIAL SUBJECT AND DISEASE CHARACTERISTICS

Subjects will be asked to come to the clinical study center for the screening visit, which may be scheduled between 28 days and 1 day prior to baseline (Day 1). The CFQ-R will be completed after informed consent was given by the subject, and prior to any other assessments scheduled for that visit. As part of the safety assessments, vital signs will be recorded, a pulse oximetry will be performed to measure oxygen saturation, and a 12-lead ECG will be recorded. Efficacy assessment tests will be performed, including sweat collection and spirometry. Blood and urine samples will be collected for clinical safety laboratory tests, serology, pregnancy test, and FSH test (if applicable). In addition, the following assessments will be done during screening: a complete check of inclusion and exclusion criteria, demographics (recording of year of birth, age and race), a general medical examination including medical and surgical history (including CF-specific medical history e.g. date of diagnosis, sweat chloride concentration prior to any treatment with a CFTR modulator, CFTR mutation, etc.) and questions about smoking habits, alcohol and drug intake, a full physical examination (including height), and weight. Finally, the subject diary will be dispensed.

All AEs (serious and non-serious) and concomitant medications will be reported continuously from the time a signed and dated ICF is obtained until the final follow-up visit.

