8.5.2. Analysis

Table 14.1.3.9: Screening and baseline disease characteristics

Continuous parameters: descriptive statistics per treatment group (and overall).

Categorical parameters: frequency tabulation per treatment group (and overall).

No formal comparison between the treatment groups is planned.

Population: the table will show

- safety
- ITT.

Table 14.1.3.10: Screening and baseline disease characteristics: Sub-group analyses

The following sub-groups will be shown:

- By target C_{trough} at Day 15
- By target C_{trough} at Day 29
- By target C_{trough} at Day 15 and 29
- By sweat chloride (from arm with greatest volume) at baseline
- By sweat chloride (mean value from both arms) at baseline
- By %FEV1 at baseline

Population: the table will show

- safety
- ITT.

Table 14.1.3.11: Screening and baseline disease characteristics: Pooled analyses

The following sub-groups will be shown:

- By target C_{trough} at Day 15
- By target C_{trough} at Day 29
- By target C_{trough} at Day 15 and 29

Population: the table will show

- safety
- ITT.

Listing 16.2.4.2: Screening and baseline disease characteristics

Listing per treatment group and per subject of all screening and baseline disease characteristics. Genotyping will be listed as well.

Population: Safety.

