8.8. EXPOSURE TO STUDY MEDICATION AND COMPLIANCE

8.8.1. Derivations

Derived parameters for GLPG2222/Placebo intakes:

- Total treatment duration (days) = (last dose administration date – first dose administration date) + 1 day.
- Total treatment duration, excluding days off drug (days): sum of all durations (last – first +1) in the drug log pages where there is a dose >0 tablets.

- Percentage days with an intake = $100\% \times \left(\frac{\text{total treatment duration,excluding days off drug}}{\text{total duration}} \right)$
- Total compliant treatment duration (days): sum of all durations (last – first +1) in the drug log pages where there is a dose with exactly 1 tablet (for cohort A) or exactly 3 tablets (cohort B).
- Percentage compliance = $100\% \times \left(\frac{\text{total compliant treatment duration}}{\text{total duration}} \right)$

The “total duration” used as denominator in the above formulae equals: (date of Day 29 visit or early termination visit) – (date of first drug intake) + 1.

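### SAP 8.5.1 subtracts the dates in the wrong order when it derives duration of CF, so programmed as written it gives a negative duration for essentially every subject

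*SAP*

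**What the plan says.** SAP 8.5.1 lists "Duration of CF (years") first among the baseline disease characteristics. The numerator reads "date of initial diagnosis}) - (\text{date of signing the ICF}) + 1" (the braces and the text command are typesetting marks). It is divided by 365.25 and "rounded to the nearest integer". For incomplete diagnosis dates the rule is "Missing day: use the first of the month. Missing month: use January".

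SAP 8.5.2 sends the section's parameters to four outputs:

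- Table 14.1.3.9, the main table, specified as "Continuous parameters: descriptive statistics per treatment group (and overall");
- Table 14.1.3.10, the same characteristics within sub-groups;
- Table 14.1.3.11, the pooled version;
- Listing 16.2.4.2, by subject.

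The three tables are shown for the safety and ITT populations, the listing for the safety population only.

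Two places in the protocol fix the order of the dates. Inclusion criterion 2 (Protocol 5.2.2) requires "A confirmed clinical diagnosis of CF and homozygous for the F508del CFTR mutation", documented in the medical record or a CF registry. Protocol 6.2 collects "CF-specific medical history e.g. date of diagnosis" at the screening visit, as history.

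**The concern.** A duration should be the later date minus the earlier one. Here diagnosis is the earlier date, and the formula puts it first. Nothing else in SAP 8.5.1 turns the sign back: there is no absolute value, and the partial-date rule moves an incomplete diagnosis date to the start of its month or year, which makes the result more negative.

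The SAP does it the other way elsewhere. Treatment duration in SAP 8.8.1 is "last dose administration date – first dose administration date) + 1 day", and AE duration in SAP 13.1.4 is stop date minus start date plus 1. Even within SAP 8.5.1, the changes in sweat chloride and %FEV1 are baseline minus screening. The CF formula is the exception, which points to a drafting slip.

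At stake is one row of the baseline tables. Its mean, median, minimum and maximum would carry the wrong sign. The minimum and maximum would also change places, so the longest-standing disease would appear as the minimum.

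**Working it through.** The plan states no numerical result for this variable, so there is no figure to reproduce. The check is to evaluate the formula literally and compare it with the reversed order.

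**Inputs.** The formula, the divisor 365.25 and the rounding come from SAP 8.5.1. The documents give no diagnosis or consent dates, so an ICF date of 1 March 2017 and a range of diagnosis dates are assumed for illustration. Let G be the number of days from diagnosis to consent.

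- As written: (−G + 1)/365.25
- Order reversed: (G + 1)/365.25

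| Assumed diagnosis date | G (days) | As written | Rounded | Order reversed | Rounded |
|---|---|---|---|---|---|
| 1 Jan 1987 | 11,017 | −30.160 | −30 | 30.166 | 30 |
| 1 Mar 1992 | 9,131 | −24.997 | −25 | 25.002 | 25 |
| 1 Mar 1999 | 6,575 | −17.999 | −18 | 18.004 | 18 |
| 1 Mar 2007 | 3,653 | −9.999 | −10 | 10.004 | 10 |
| 1 Mar 2015 | 731 | −1.999 | −2 | 2.004 | 2 |

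For the second row: (−9,131 + 1)/365.25 = −9,130/365.25 = −24.997, against (9,131 + 1)/365.25 = 9,132/365.25 = 25.002.

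**Where the negative sign stops.** Rounding removes it for short gaps:

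- G = 184: −183/365.25 = −0.501, which rounds to −1.
- G = 183: −182/365.25 = −0.498, which rounds to 0.
- G = 2 to 183: negative before rounding, 0 after.
- G = 1: 0/365.25 = 0. G = 0: 1/365.25 = 0.003. Both round to 0.

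So any diagnosis 184 or more days before consent is reported as −1 or lower, and any shorter gap is reported as 0.

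**The +1 term.** In the written order it shortens the magnitude where it should lengthen it. The two magnitudes differ by 2 days: 2/365.25 = 0.0055 years. Over gaps of 0 to 19,999 days, the rounded magnitude differs for 110 of the 20,000 values (110/20,000 = 0.55%), all near a half-year boundary.

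**The case against.** The best case for leaving this alone is that it is a slip nobody would carry through. The label makes the intent plain, and a column of negative durations would stand out in the first draft output. SAP 6.2 lists procedures for quality of deliverables and for QC, and SAP 6.3 refers to separate mock outputs that may show what is meant. Much of this stands: a wrong published table is unlikely. It does not correct the text, however. A programmer who fixed the sign would be departing from a stated derivation rule, and SAP 7.2 records no change to the planned analyses.

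A reader might infer more than the documents support, in four ways:

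- *That every subject gets a negative value.* Rounding gives 0 for a diagnosis 183 days or less before consent. That should be rare in adults with a documented diagnosis, but the documents give no distribution of diagnosis dates.
- *That the misplaced +1 is an error of its own.* It amounts to 2 days, and rounding almost always removes it. The sign is the real fault.
- *That all four outputs are affected in both populations.* The listing is specified for the safety population only.
- *That efficacy or safety results are affected.* The ANCOVA in SAP 7.1.3 uses treatment and the baseline value of the outcome. Duration of CF is not among the sub-group factors in SAP 3.4 or the endpoints in SAP 1.2, and SAP 8.5.2 plans no formal comparison between groups. Table 14.1.3.10 would show the wrong duration within sub-groups, but nobody would be placed in a different one.

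The formula is a typeset fraction read from a PDF. It came through complete, with both terms labelled, and nothing suggests that they were swapped in reading.

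**Conclusion.** Wrong as written. The subtraction is reversed, and no other section of the SAP or protocol corrects it. Applied literally, it changes the sign of the duration for every subject diagnosed 184 or more days before consent, which in this population should be essentially all of them. The size in years is practically unchanged. The consequence is confined to a descriptive row in Tables 14.1.3.9 to 14.1.3.11 and an entry in Listing 16.2.4.2, so this is a minor text correction.

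The conclusion rests on diagnosis preceding consent, which follows from the inclusion criterion and from the date being collected as medical history. The calendar dates above are illustrative, and the sign does not depend on them.

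**What to change.** In SAP 8.5.1, replace the formula with (ICF date − diagnosis date + 1)/365.25, and keep the rounding and the partial-date rule as they are. Correct the formula itself and do not just drop the minus sign from the output: dropping it would leave the magnitude 2 days short of the SAP's inclusive convention for durations. If the derived-dataset specification or the mock outputs repeat the formula, change it there too.

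The cost is one line of SAP text. No data collection, trial conduct, sample size or inferential analysis changes. If the outputs have already been programmed to the written rule, the three tables and the listing need to be rerun.
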